## 0.0 Abstract

**[Note: The current Central IRB application refers to Phase 2. Grey shaded elements refer to Phase 1 which was approved by the Institutional Review Board for Baylor College of Medicine and Affiliated Hospitals (IRB of record for the Michael E. DeBakey VA Medical Center, Houston, TX) and the Houston VA Research & Development Committee. See Protocol Number H-33772 approval letter (Attachment 1)]**

**0.0.1. Background:** Diabetes mellitus is a highly prevalent chronic condition, affecting one in five Veterans who use the Veterans Affairs (VA) health care system. Self-management skills are critical for controlling diabetes and reducing its cardiovascular sequelae. Providing diabetic patients with effective self-management training and support can be challenging due to time constraints at primary care encounters and limited clinician training with behavior change. We have previously demonstrated that a group-based, VA primary care intervention to help patients set highly effective, evidence-based diabetes goals had a positive impact on both diabetes self-efficacy and hemoglobin (Hb) A1c levels. This study aims to evaluate the process of implementing a collaborative goal-setting intervention personalized to patient activation and health literacy levels (i.e. Empowering Patients in Chronic Care [EPIC]) into routine PACT care and to evaluate the effectiveness this intervention relative to usual care.

**0.0.2. Objectives:** Specific Aim 1: Assess effective processes for and costs associated with implementing a collaborative diabetes goal-setting intervention personalized to patient activation and FHL (i.e., EPIC) into the routine workflows of PACTs. H1: Formative measures within the PARIHS framework (evidence, context, facilitation) will be associated with implementation of EPIC (defined by reach, adoption, cost effectiveness, and fidelity measures) into routine PACT care. Specific Aim 2: Evaluate the effectiveness of delivering collaborative goal-setting personalized to patient activation and FHL on clinical (HbA1c) and patient-centered (Diabetes Distress Scale) outcomes among enrolled eligible patients. H2: Patients receiving collaborative goal-setting personalized to activation and FHL levels will have significant improvements in a) HbA1c and b) Diabetes Distress Scale levels, respectively, post-intervention (4-months) compared with patients receiving enhanced usual care. H3: Patients receiving collaborative goal-setting personalized to activation and FHL levels will maintain significant improvements after a maintenance period in a) HbA1c and b) Diabetes Distress Scale levels at 10 month follow-up, respectively, compared with patients receiving enhanced usual care.

**0.0.3. Methods:** In Phase 1 of the study, we will conduct a formative evaluation that includes 33-48 key informant interviews with VISN 12 and Houston-based leadership, clinicians, and staff. This evaluation will identify how group and one-on-one sessions of EPIC can best be implemented into routine workflows of PACT. In Phase 2, we will conduct a randomized clinical trial enrolling Veterans with poorly controlled diabetes defined by average hemoglobin A1c of  $\geq$  8% to receive EPIC or enhanced usual care. To meet a minimum target of 284 Veterans to be randomized for analysis, an estimated population of 428 Veterans will be enrolled, including screen failures, from across participating facilities (approximately 160 from Hines, 200 from Jesse Brown, and 68 between Houston and Lovell). Randomized subjects will be allocated

[name]\_Point-of-Care Health Literacy and Activation Information to improve Diabetes Care Version 3, February 17, 2016.

evenly between EPIC and enhanced usual care (EUC). EPIC consists of six 1-hour group sessions focusing on 1) Your Health, Your Values, 2) Diabetes ABCs, 3) Setting Goals and Making Action Plans, 4) Communication with Your Health Care Provider, 5) Staying Committed to Your Goals, and 6) Reviewing and Planning for the Future. After each group session, a one-on-one session between a designated PACT member and patient participants will focus on collaborative goal-setting. Designated PACT members will be trained to personalize goal-setting using patient-reported activation and health literacy data. We will collect laboratory and survey data at baseline, post-intervention, and post-maintenance phase. We will evaluate the effectiveness of personalized goal-setting compared to enhanced usual care on clinical (e.g., hemoglobin A1c) and patient-centered (e.g., Diabetes Distress Scale) outcomes.

## List of Abbreviations

AHRQ	Agency for Healthcare Research and Quality
ANCOVA	Analysis of Covariance
Ask Me 3	Patient education program designed to improve communication between patients and health care
Atlas-ti	Qualitative data analysis software
BCM	Baylor College of Medicine
CBOC	Community- Based Outpatient Clinic
CBT	Cognitive Behavioral Therapy
CERT	Center for Education and Research on Therapeutics
CREATE	Collaborative Research and Enhance and Advance Transformation an Excellence Initiative
CSQ-8	Client Satisfaction Questionnaire
DDS	Diabetes Distress Scale
CDW	Corporate Data Warehouse
Delphi	Structured communication technique created by RAND
Deyo	Comparative studies of comorbidity and multimorbidity measures
DSME	Diabetes Self-Management Education
DSM-IV	Diagnostic and Statistical Manual of Mental Disorders
EPIC	Empowering Patients in Chronic Care
EQ-5D	Standardized instrument for use as a measure of health outcome
EUC	Enhanced Usual Care
FHCC	Federal Health Care Center
FHL	Functional Health Literacy
GET-D	Goal-Setting Evaluation Tool for Diabetes
HbA1c	Glycated hemoglobin
HPDP	Health Promotion and Disease Prevention
HSR&D	Health Services Research and Development
ICC	Intra-class correlation
ICD-9-CM	International Statistical Classification of Disease and Related Health Problems, 9th Revision
ICER	Incremental cost-effectiveness ratio
IIR	Investigator Initiated Research
IRB	Institutional Review Board
ISO	Information Security Officer
IQuEST	Center for Innovations in Quality, Effectiveness and Safety
JBVAMC	Jesse Brown VA Medical Center
MEDVAMC	Michael E DeBakey VA Medical Center

MINANALYZE	Analyze imputations and generates valid statistical inferences
MINI	Short structured interview used to identify mental health conditions
MIRECC	Mental Illness Research, an Clinical Center
MPlus	Statistical Software
ORCA	Organizational Readiness to Change Assessment
P.A.R.T.	Prepared, Ask, Repeat, Take Action
PACTs	Patient-Aligned Care Teams
PAM	Patient Activation Measure
PARIHS	Promoting Action on Research in Health Services
PCP	Primary Care Provider
PEPPI	Perceived Efficacy in Patient-Physician Interactions Questionnaire
PHI	Protected Health Information
PI	Principal Investigator
PII	Personally Identifiable Information
Proc MI	Performs multiple imputation of missing data
Proc Mixed	Enables use of fitted models to make statistical inferences about the data
QUERI	Veteran Affairs Diabetes- Quality and Enhancement Research Initiative
RAND	Research and Development
RCS	Records Control Schedule
RCT	Randomized Control Trial
RE-AIM	Dimensions of Reach, Efficacy, Adoption, Implementation, and Maintenance
REALM	Rapid Estimate of Adult Literacy in Medicine
SAS	Statistical Analysis Systems
SKILLD	Spoken Knowledge In Low Literacy in Diabetes Scale
S-TOFLA	Test of Functional Health Literacy in Adults
SQL	Structured Query Language
UNIX	Multi-user computer operating system
VA	Veterans Affairs
VAMC	Veteran Affairs Medical Center
VINCI	VA Informatics and Computing Infrastructure
VISN	Veterans Integrated Service Network

## 2.0 Introduction

Diabetes mellitus affects one in five Veterans who use the Veterans Affairs (VA) healthcare system. Serious cardiovascular diseases, like stroke and myocardial infarction, arise in many diabetic patients and account for most of the mortality attributed to diabetes. Self-management skills are critical for controlling diabetes and reducing its cardiovascular sequela. Providing diabetic patients with effective self-management training and support can be challenging due to time constraints at primary care encounters and limited clinician training with behavior change. We have previously demonstrated that a group-based, VA primary care intervention to help patients set highly effective, evidence-based diabetes goals had a positive impact on both diabetes self-efficacy and hemoglobin (Hb) A1c levels. This study applied collaborative goal-setting theory. to empower patients to make diabetes self-management goals and to facilitate goal attainment at subsequent group visits. Unlike most educational programs that demonstrate regression to the mean at 4-months, participants in the goal-setting treatment arm sustained HbA1c improvements for nine months after the active intervention. However, ongoing improvements in goal-setting quality were not seen when participants returned to routine primary care and the maintenance of goal-setting activities remained modest at 1-year among intervention participants, suggesting the need to further refine the collaborative goal-setting program.

The effectiveness and maintenance of goal-setting interventions may be enhanced by incorporating VA staff into the collaborative goal-setting process. With appropriate training, existing VA personnel can enhance diabetes outcomes by integrating personalized information about patients' reported self-care capacity (i.e., functional health literacy [FHL]) and motivation (i.e., patient activation measure) into the collaborative goal-setting process. In an HSR&D-funded pilot study, we demonstrated that brief measures of FHL and patient activation synergistically predicted HbA1c levels. Thus, assessing patients' FHL and level of activation within the VA PACT context may allow PACTs to better personalize goal-setting among Veterans with diabetes. While validated, practical measures of FHL and activation levels exist; they have not been effectively integrated into routine PACT practice and shown to impact patient outcomes. If such measures were integrated at the point of care (i.e., when primary care providers and patients are developing collaborative diabetes goals), PACT clinicians could personalize goals and action plans within patients' particular limitations and preferences for involvement.

[figure not shown]
### 2.A. Background and Conceptual Model

**2.A.i. Self-management training and support are key to improving the health outcomes of Veterans with treated but uncontrolled diabetes.** At any given time, over one million Veterans are receiving health care services for diabetes, and many suffer adverse vascular outcomes, such as myocardial infarction, blindness and peripheral artery disease. Diabetes control, characterized by reductions in hemoglobin (Hb)A1c, blood pressure, and cholesterol levels, is directly associated with lower morbidity and mortality. Because diabetes is a self-managed condition, achieving diabetes control requires patient involvement in most aspects of treatment planning and management. As a result, self-management training and support is a cornerstone of evidence-based treatment for diabetes in primary care; this practice is endorsed by national standards from the American Diabetes Association, the VA-Department of Defense Management of Diabetes Mellitus Clinical Practice Guidelines, and the VA Diabetes-Quality Enhancement Research Initiative (QUERI).

**2.A.ii. Delivering self-management training and support in routine primary care can be difficult, and traditional education programs are handicapped by outdated methods.** Most prior self-management interventions have focused on didactic education rather than personalized treatment-planning and development of problem-solving skills. The traditional primary care visit is not an ideal setting to develop or support self-management skills due to time constraints and the need for team-based approaches. The move towards patient-centered medical homes (referred to as Patient-Aligned Care Teams [PACT] within VA primary care) provides an excellent opportunity to efficiently and effectively integrate diabetes self-management training and support into primary care. The goal of VA PACTs is to provide integrated, comprehensive, Veteran-centered primary care tailored to individual characteristics, values, and goals.

**2.A.iii. Empirically supported, theory-driven methods of diabetes self-management exist, but more data are needed on wide-spread dissemination and integration into primary care.** Collaborative Goal-Setting (Figure 1) is an empirically-supported theory for enhancing human effort, motivation, and persistence toward an outcome. It encourages development of skills and problem-solving strategies for overcoming obstacles when challenges arise. When adapted to a chronic illness context (main pathway in Figure 1), collaborative goal-setting between patients and clinicians results in greater performance of self-management action plans and improved clinical and patient-centered outcomes. Recent clinical trials have firmly established the clinical effectiveness of diabetes self-management training and support based on goal-setting theory. However, there is considerable variability across studies, and an Implementation Science approach is needed to resolve gaps in our understanding of how large-scale goal-setting interventions can be effectively implemented into routine workflows and processes of busy health care providers.

One of these critical gaps is how best to integrate self-management training and support into the routine structure of VA PACTs. We have developed and tested a collaborative goal-setting intervention in a trial of two diabetes group clinic interventions: 1) standard diabetes and nutrition education and 2) our collaborative goal-setting approach. The goal-setting approach focused on setting high quality self-management goals and action plans linked to diabetes clinical outcomes (Figure 1). Participants were also taught communication skills to elicit feedback and support about their action plans. The methods used in this study evolved from prior work developing our model of patient empowerment and goal-setting. The intervention provided patients with training (group sessions) and support (one-on-one sessions) with diabetes goal-setting. Participants randomized to collaborative goal-setting had clinically significant improvements in HbA1c levels post-intervention and at 1-year follow-up compared to those randomized to the education group. These outcomes were mediated by improvements in self-efficacy related to diabetes self-management tasks.

**2.A.iii.a Despite these important successes, our prior collaborative goal-setting intervention had limitations.** First, ongoing improvements in diabetes self-efficacy and outcomes were not seen when participants returned to routine primary care after the intervention. Second, the maintenance of goal-setting behaviors remained modest at 1-year among participants. These limitations may reflect the fact that we relied on trained research staff to conduct the full intervention and patients’ primary care providers had little involvement in the goal-setting process. In addition, the prior study occurred prior to the widespread rollout of PACTs across VA. The proposed study addresses these limitations by implementing the intervention into routine PACT care and using a PACT members to set personalized goals.

**2.A.iv. VA PACT realignment creates an opportune setting for involving primary care providers in collaborative goal-setting.** The core team or “teamlets” within PACT consist of the Veteran patient, a primary care provider, a nurse care manager, a clinical associate (e.g., licensed practical nurse or health technician) and a clerk. Several teamlets work closely with a larger multidisciplinary team that includes pharmacists, social workers, nutritionists, specialist providers, and staff, including behavioral health specialists. These specialists assist patients with self-management goals and developing problem-solving action plans (i.e., health coaching). Goal-setting and action plans are key elements of effective diabetes self-management. Indeed, the objectives of diabetes goal-setting are completely consistent with the patient-centered mission of PACT. Given realignment of VA primary care towards PACT, dissemination of an evidence-based method for delivering collaborative goal-setting is the right intervention at the right time to improve patient-centered and clinical outcomes for diabetes care.

**2.A.v. Further enhancements of collaborative goal-setting can be achieved by integrating personalized information about patients’ activation and health literacy levels.** The success of goal-setting (see predisposing patient factors in Figure 1) is influenced by patient’s motivation (possessing the skills, beliefs, activation and confidence to manage one’s health), and capacity (the ability to process and understand basic health information and carry out health decisions). From a conceptual perspective, motivation and capacity can be measured using scales of patient activation and functional health literacy (FHL), respectively.

Both FHL and activation play critical roles in achieving diabetes control. Patients with uncontrolled diabetes tend to be passive (low activation levels) and have limited FHL. Studies show that diabetic patients with inadequate FHL are less likely to achieve glycemic control and experience greater difficulty with self-management tasks necessary for diabetes control. Similarly, patients with lower levels of activation also have poorer diabetes self-management and medication adherence. In a prior study, a literacy-focused diabetes

intervention was effective in improving glycemic control and self-efficacy in patients with uncontrolled diabetes. Another study found that tailoring self-management coaching to activation levels in diabetic patients was associated with improvements in activation, blood pressure, and low density lipoprotein control.

In an HSR&D-funded pilot study ([name], PI), we demonstrated that brief measures of FHL and patient activation can be elicited among diabetic patients, and those with high scores on both measures had significantly lower HbA1c levels ( $p < .005$ ). In another study, our team explored how FHL and activation impact preferences for collaborative decision making among chronically ill Veterans and demonstrated that these preferences are potentially mutable when clinicians consider FHL. Given these findings, personalizing diabetes goal-setting using **both** activation and FHL is an important next step in improving collaborative goal-setting between patients and PACT members. We anticipate that addressing both activation and FHL will have a synergistic effect, leading to higher quality goals, action plans and ultimately, better diabetes outcomes.

**2.A.vi. Delivering FHL and activation information and training PACT members to personalize goal-setting using this information can improve diabetes outcomes.** Health care providers frequently have difficulty identifying patients with limited FHL; therefore, delivering information about FHL to providers during patient-provider encounters may enhance communication and decision-making. However, work in this area is limited. In a study by Seligman et al., physicians who were notified of their diabetic patients' limited FHL prior to a visit reported greater use of strategies to improve communication about disease management, but were less satisfied with encounters due to feelings of inadequacy about using FHL information. Importantly, participating physicians received little education about how to use FHL information to guide interactions. Our team has experience training research and PACT members in the process of collaborative goal-setting, and we are currently testing a telephone delivered intervention with PACT members trained to use goal-setting in Veterans with diabetes and depression ([name], IIR 10-135). We posit that personalized FHL and activation information provided at the point of care (i.e., when PACT members evaluate the data and have goal-setting discussions) can improve the effectiveness of goal-setting if PACT members are appropriately trained on how to best integrate this personalized data into the collaborative goal-setting process. Further research is needed to explore the impact of personalized, collaborative goal-setting on clinical and patient-centered outcomes.

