The **third component** will focus on how to set high quality collaborative goals and action plans. After participants learn the aspects of high quality goals (i.e., specific, realistic, deadline oriented), they will proceed through goal-setting and action planning role plays with a fellow trainee or local research staff. Following this exercise, the trainer will lead the group in a discussion to clarify the lessons from the role play; this discussion will incorporate the health coaching techniques discussed in training component two. This training sequence has been developed, tested, and modified by Bodenheimer and colleagues to train health professionals in goal-setting and action planning to facilitate diabetes-related behavioral change.

With this foundation, participants will learn strategies to personalize goal-setting and action planning in **the fourth component** of the training session. First, we will introduce the concepts of patient activation, (i.e., possessing the knowledge, skills, beliefs, and confidence to manage one’s health) and health literacy (use of “conversational language” (e.g., “sugar” for glucose). We will emphasize how these constructs relate to the patient’s motivation to participate in diabetes self-management activities and how to improve communication strategies for patients with low literacy levels. (see Table 8). We will discuss characteristics associated with the spectrum of activation levels ranging from low to high. Patients with low activation are often overwhelmed and not prepared to actively participate in their health care. Conversely, patients with high activation are goal-oriented and have developed effective self-management and problem-solving skills. However, despite high levels of activation, these patients may have difficulty maintaining healthy behaviors when faced with life stressors. Next, participants will learn specific strategies to assist patient-participants at different levels of activation. For example, with lower activation levels, we will instruct participants to focus on single goals that are important to the patient while providing extra encouragement to help build self-confidence, and reinforce the importance of participation. With patients at high activation levels, we will train employee participants to center their interactions with patients on maintaining self-management behaviors, effective problem-solving to prevent relapse, and adding to existing action plans.

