We will conduct exploratory analyses to examine associations between implementation measures (RE-AIM elements in table 5) and study outcomes following the conclusion of Phase 2. For example, for all eligible patients, within each PACT demographic characteristics will be compared between enrolled and non-enrolled patients using chi-square tests and independent samples t-tests. Fisher's Exact Test and the Wilcoxon Mann-Whitney tests will be used where appropriate. An index of reach representativeness will be calculated for each PACT which will then be correlated with post-intervention outcomes, controlling for respective baseline values. Similarly, for all PACTs sampled, PACT characteristics (e.g., panel size) will be compared between sampled and non-sampled PACTs using chi-square tests and independent samples t-tests. An index of adoption representativeness will be calculated for each PACT which will then be correlated with post-intervention outcomes, controlling for respective baseline values. Additionally, for patients receiving the EPIC intervention within each PACT, post-intervention HbA1c will be separately regressed on 1) the proportion of group sessions attended, 2) the proportion of individual sessions attended, and 3) baseline objective ratings of the group leader's fidelity. These models will control for baseline HbA1c and will be conducted using ANCOVA methods. Predictors that are significant at  $p < 0.25$  will be included in a multiple linear regression to examine both collective and unique predictors of post-intervention HbA1c levels (once again controlling for baseline HbA1c). Similar univariate and multivariate models will be formed to predict post-intervention DDS.

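### The exploratory session-attendance models within EPIC adjust only for the baseline outcome; baseline activation and health literacy, both already collected, should be added and the results reported as associations

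*Combined protocol and SAP*

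**What the plan says.** Section 5.6.C, Specific Aim 1, introduces the analysis with "We will conduct exploratory analyses to examine associations between implementation measures" and study outcomes. For EPIC patients, "post-intervention HbA1c will be separately regressed on 1) the proportion of group sessions attended", then on the proportion of individual sessions attended, then on the group leader's fidelity rating. On adjustment: "These models will control for baseline HbA1c and will be conducted using ANCOVA methods". Predictors with p < 0.25 go into one multiple regression, again with baseline HbA1c as control. DDS is to be modelled in a similar way.

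Elsewhere the protocol describes the factors left out:

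- Section 2.A.v, on functional health literacy and activation: "those with high scores on both measures had significantly lower HbA1c levels".
- Section 2.A.v, on activation: "patients with lower levels of activation also have poorer diabetes self-management and medication adherence".
- Section 5.1.F.ii: "Patients with low activation are often overwhelmed and not prepared to actively participate in their health care". The same section ties both constructs to the patient's "motivation to participate in diabetes self-management activities".

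Section 5.1.I.c and Table 10 list PAM and FHL as baseline covariates. They are gathered during the randomization call, before any session takes place.

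**The concern.** How many sessions a patient attends is decided after randomization and largely by the patient. If activation or literacy influences both attendance and later HbA1c or distress, patients who attend more will do better even if the sessions have no effect. Adjusting for baseline HbA1c removes only the part of that influence already present at baseline. Whatever activation does to self-management over the following months stays in the attendance slope, and pushes it in the favorable direction.

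What is at stake is the interpretation of a secondary implementation result. A negative attendance slope is easily taken to show that more sessions give better control, and Table 10 places group attendance among the intervention mediators and moderators. The plan measures two plausible common causes in advance and does not use them here.

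**Working it through.** **Number of patients.** Section 5.6.A starts from 100 per arm, an intraclass correlation of 0.0183, 12 patients per PACT and 15% attrition.

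- Design effect: 1 + (12 − 1) × 0.0183 = 1.2013.
- 100 × 1.2013 = 120.1, taken as 120.
- 120 / 0.85 = 141.2, rounded up to 142 per arm, 284 in total. The plan's figure reproduces.
- EPIC patients with outcome data: 142 × 0.85 = 120.7, about 121, if PACTs are pooled.

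The documents give no figure for the attendance analysis and no correlation of activation or literacy with attendance or with later HbA1c. Everything below is conditional on assumed values, with a true session effect of zero.

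**Structure A.** Let a be the correlation of activation with attendance, and b its correlation with post-intervention HbA1c given baseline. With activation omitted, the spurious partial correlation of attendance with outcome is r = a × b, and the test statistic is centered at √(121 − 3) × r / √(1 − r²). For a = 0.3 and b = −0.3, r = −0.09 and the center is 10.86 × (−0.09) / 0.996 = −0.98, which gives rejection of about 16%. Simulation (20,000 runs per setting) gives:

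| a | b | p < 0.05 | p < 0.25 |
|---|---|---|---|
| 0.2 | −0.2 | 7.3% | 30% |
| 0.3 | −0.2 | 9.6% | 34% |
| 0.3 | −0.3 | 16% | 45% |
| 0.5 | −0.3 | 37% | 69% |

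**Structure B.** All variables are standardized. The baseline-to-post HbA1c slope is 0.5, activation correlates −0.2 with baseline HbA1c, and g is the activation effect on post HbA1c given baseline. The spurious slope is g × a(1 − 0.04) / (1 − 0.04a²). For a = 0.3 and g = −0.2 this is −0.2 × 0.288 / 0.9964 = −0.058 SD of HbA1c per SD of attendance. Simulation (3,000 runs per setting) gives:

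| a | g | mean slope | p < 0.05 | p < 0.25 |
|---|---|---|---|---|
| 0.1 | −0.1 | −0.009 | 5.4% | 26% |
| 0.3 | −0.2 | −0.057 | 11% | 37% |
| 0.4 | −0.3 | −0.118 | 34% | 67% |

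**With baseline activation in the model**, the mean slope is within 0.003 of zero. Rejection is about 5% (4.6% to 5.7% in the settings with a link) and about 25% of trials pass the p < 0.25 screen. This follows by construction, since activation is the only confounder simulated. It shows what adjustment does about activation and nothing about confounders that are not measured.

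**The case against.** **The analysis is labelled exploratory and speaks of associations.** This stands. It limits the importance of the point, but it does not explain leaving out measured baseline factors that the protocol itself names.

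**No data link activation or literacy to session attendance.** This also stands. The participation statements come from a description of staff training and concern taking part in one's care generally. The research findings in section 2.A.v concern HbA1c, self-management and medication adherence. The pilot finding relates scores to HbA1c level, part of which baseline adjustment absorbs. The case is weaker for literacy than for activation.

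**Enrollment and tailoring may weaken the link.** Participants came to an introductory meeting and reported no transport, availability or peer-group barrier, and sessions are adapted to low activation and low literacy. The moderate correlations above may therefore be too high.

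**Other lines might supply the covariates.** Section 5.6.A says in general terms that models will be adjusted for patients' baseline covariates. That line sits in the sample-size section and does not override the explicit covariate statement in 5.6.C. The p < 0.25 rule under Specific Aim 2 selects variables that differ between EPIC and EUC, so it does not address confounding within EPIC. The multiple regression does adjust the session and fidelity terms for one another, but it adds no further patient characteristic.

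**The figure of 121 assumes pooling.** The text refers to EPIC patients within each PACT. With 142 spread over 24 PACTs that is about 6 patients each, too few for separate models, so pooling is the workable reading.

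**Stronger readings.** A reader might infer that VA would use these models to set a required number of sessions. No section says so or plans a dose claim. A reader might also ask for an instrumental-variable estimate with arm as instrument. With EUC sessions set to zero, that only divides the intention-to-treat difference by mean attendance. It cannot separate group from individual sessions and carries no dose-response information. It also assumes that arm acts only through sessions, which is doubtful because EUC has its own referral and materials.

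**Conclusion.** The point holds as a modest, inexpensive improvement to an exploratory analysis. The attendance models omit two baseline factors that the protocol relates to diabetes control and, more loosely, to motivation to participate. The attendance slope may partly reflect them.

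The size is not known. Over the assumed range, false rejection at 0.05 runs from about 5-7% with weak links, which is little or no inflation, to 34-37% with moderate ones. A middle case (0.3 and −0.2) gives about 10-11%. These figures rest on assumed correlations, pooled data on 121 patients and no true session effect.

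It would be wrong to infer that the effectiveness results are compromised. H2 and H3 compare randomized arms and do not use these models. Nor do the documents show that any attendance association would be spurious. They show only that the planned models could not separate it from activation and literacy.

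**What to change.** In section 5.6.C, Specific Aim 1, prespecify baseline PAM and FHL as fixed covariates in every attendance model for HbA1c and DDS. This covers the single-predictor models and the multiple regression, and the two covariates should stay in regardless of the p < 0.25 screen. State which literacy score is used, since section 5.1.I.c names both three brief questions and the SKILLD. Add a sentence that the attendance results are associations and will not be reported as effects of session dose.

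The cost is SAP wording and two more covariates, with no new data. Unmeasured confounding of attendance remains, so the caution on interpretation is needed even after adjustment.
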